6.1. Potential Risks

Potential risks to participants, and their likelihood and seriousness to the human subjects: The main risk of participating in this study is the loss of confidentiality. While many participants may have disclosed their HIV status to their family, we consider loss of confidentiality an important risk of the study. The loss of confidentiality may lead to disclosure of HIV infection or disclosure of drinking status. Stigma associated with such disclosure may include social harms such as disruption of family (e.g., breakup of couples following HIV detection in one spouse), discrimination (e.g., a loss of employment or status in community), physical harm such as domestic violence (e.g., acts of physical violence directed at people who have been diagnosed with HIV), and psychological harm such as embarrassment (e.g., being questioned by family members about alcohol use). There may be some discomfort with the nature of the interviews, since alcohol use will be discussed. There is also the very slight but present chance of a breach of confidentiality inherent in any study that handles confidential data.

Other potential risks of participating in the study include:

- Psychological stress could be caused by the interview in which participants will be asked sensitive questions regarding substance use and HIV status and progression. Distress caused by the length of the interview is also possible.
- Phlebotomy associated risks include bruising, bleeding, infection, phlebitis, and pain. Bruising is common, minor pain with needlestick is universal, the other risks are rare.
- Biohazard containment is an additional risk, as the transmission of HIV and other blood-borne pathogens can occur through contact with contaminated needles, blood, and blood products.
- There is a risk of a 3rd party (including makers of the computer software and others) intercepting both research and non-research data.
- There is a risk of additional costs to cell phone usage for participants that are not anticipated.

Alternative procedures: The alternative is to either not consent to the study or to withdraw from the study at any time after consented. We will be clear with participants that there is no obligation to enroll in or continue with the study. Any participant may decline any study procedure at any time—this will not affect the person's ability to receive

care at any HIV clinic. Any potential study participant who does not wish to enroll in the study but wishes to learn more about their alcohol consumption will be referred to their doctor.

6.2. Protection against risks

Planned procedure for protection from risks due to loss of confidentiality: We will implement the following procedures to protect participants against the risks of loss of confidentiality:

- We will discuss the possibility of HIV, or alcohol-related stigma with the potential participants during the informed consent process for the study. We will ask potential participants to think about persons in their family, group of friends, neighborhood, or workplace, who don't know their HIV status, and how they might react to discovering that the participant is infected with HIV, or drinks alcohol. Enrollment will be deferred for those who are unsure about ramifications of participating. Persons who decline or defer enrollment in the study will be assured that this will not affect their HIV care.
- We will ensure that all study visits and telephone calls for tracking or study visit reminders, may be deferred for any reason and that participation in the study may be ended at any time. Telephone calls may be ended at any time with a pre-agreed upon word or action. Study staff will be trained to apply the same measures of confidentiality and sensitivity during phone calls as they do with all other data collection activities.
- We will provide referrals to all participants and persons considering enrollment to social support services provided by the MRRH Counseling Program, as desired. These services include the option of participating in support groups where issues of disclosure can be discussed, and the individual can learn from peers about high-risk disclosure situations and how to minimize risk.
- To ensure confidentiality of participation, all instruments, forms, and biologic specimens will be coded with a unique participant identifier that renders the data anonymous to persons outside the study. All data will be kept in locked cabinets and on secure servers. Research records will be kept confidential to the level allowed by law. Records with identifying information, such as contact information and consent forms, will be stored separately from survey information. No individual identities will be used in any reports or publications.
- All staff in contact with participants and/or data will be trained on procedures for maintaining privacy and will sign a pledge of confidentiality. They will also take the NIH online human subjects training courses.
- We will provide participants with a small card containing information on how to contact the local field staff to report incidents such as HIV-related disruption of families, acts of discrimination, and physical harm. These cards will not identify the study as a study of alcohol use, or of persons with HIV. This information will also be written on the take-home consent form.
- Study activities will be conducted in English or Runyakole (the local language) in the language that the participant feels most comfortable with.

Planned procedure for protection from risks due to psychological distress: The RAs will be trained to address these issues with a calm, non-judgmental attitude. Study activities will be conducted in English or Runyakole (the local language) in the language that the participant feels most comfortable with. At the participants' request, we will refer patients for medical alcohol detoxification and support groups conducted by the Department of Psychiatry at MUST. These referrals are a standard part of care at the ISS clinic. These minimal risks are not likely and will be minimized further by only selecting participants who understand the study and are willing to participate.

Planned procedure for protection from risks due to phlebotomy: Trained RAs or laboratory technicians will collect all specimens using standard sterile procedures. The phlebotomist will report any complications resulting from blood draws to the field study coordinator, who will make an immediate report to the Principal Investigator. The Principal Investigator will take responsibility for reporting such AEs to the relevant IRBs and NIH within ten days.

Planned procedure for protection from risks due to lack of biohazard containment: As the transmission of HIV and other blood-borne pathogens can occur through contact with contaminated needles, blood, and blood products, appropriate blood and secretion precautions will be employed by all personnel in the drawing of blood and shipping and

handling of all specimens for this study, as currently recommended by the Centers for Disease Control and Prevention and the NIH. Personnel will be trained in and follow standard laboratory procedures to minimize the risk of contamination.

Planned procedure for protection from risks due to 3rd party intercepting participant's data: We plan to institute the following data security controls that prevent interception of information issues as follows:

- The cell phone data will be kept only by cell phone number and unique study identifier that renders the data anonymous to persons outside the study. All SMS/IVR messages will require authentication codes for access. The web-based databases will be password protected and encrypted. All data transfers to servers at UCSF or MUST will occur via an encrypted internet connection and data will be stored on secure UCSF servers that are password-protected and encrypted.
- We plan to institute the following data security controls in general:
 - Data storage safety: The SMS/IVR data (accessed only with an authentication code) will be stored temporarily on participant's phones until the participant deletes them. The SMS/IVR data will also be stored temporarily on secure, password-protected and encrypted web-based databases until they are transmitted to our research team at UCSF. All servers storing EXTEND study data will be encrypted. Thus, all data transfers of study data, from Uganda to servers at UCSF, will occur via this encrypted internet connection, and data will be stored on secure UCSF servers that are also password-protected and encrypted. Once transmitted, data will be stored via secure, password protected, and encrypted files, identified only by the study ID, on a password protected network computer at the research study offices at UCSF. All data transfers to servers at UCSF will occur via an encrypted internet connection and data will be stored on secure UCSF servers that are password-protected and encrypted.
 - All data transfers to servers at UCSF will occur via an encrypted internet connection and data will be stored on secure UCSF servers that are password-protected and encrypted.
 - UCSF IT risk assessment and data safety measures: We will have a contract with any entity engaged in implementing our research study prior to commencing their services. The contracts will include Terms of Agreement and/or Privacy Policy to be reviewed by the UCSF IT department as well as the UCSF contracts and grants offices. These offices will continue to review updates of the agreement as needed. We will defer to the MUST IRB in Uganda on determining how the study participants will be informed that the data is subject to the set terms of agreement, which may change over time. However, we will address these issues broadly in the informed consent process.
 - Data will not be shared including contacts, texts, geo-location information, photos or other data from any of the devices used during our research study by the research team or by the study participants, with 3rd parties in both Uganda and the United States.
 - We will discuss the risks to confidentiality in engaging in SMS/IVR system in the informed consent processes and again during SMS/IVR training with participants. The SMS/IVR system will include authentication codes (PIN#s) so that only the intended participant will access the SMS/IVR messages. In addition, we will train participants to delete the SMS at the end of each session so they cannot be viewed by others using the phone. We will not identify the study as associated with the HIV clinic in any message. The cell phone data will be kept only by cell phone number and unique study identifier that renders the data anonymous to persons outside the study. All data transfers to servers at UCSF or MUST will occur via an encrypted internet connection and data will be stored on secure UCSF servers that are password-protected and encrypted.

Planned procedure for protection from risks due to additional costs to participant's cell phone use: We do not anticipate that participants will incur additional costs in cell phone charges as a result of our study. It is free to receive calls and SMS messages on Ugandan phones, thus the IVR sessions will be free, and participants can receive calls and SMS messages even if the phone has no "air time" (pre-loaded credit). The SMS sessions will require a small amount of air time to enable participants to send answers to the SMS questions, but we will automatically load ("top up")

participants' phones with air time before SMS sessions. The expected value of the cell phone credit will not exceed the expected cost of the SMS charges and will occur at the time of use so as not to be viewed as coercive. Our technology platform will be programmed to receive free text replies from participants via SMS, or a voice message from participants (as an MP3 file) via IVR, allowing for open-ended questions and responses. In addition, participants will be trained to 'flash' (calling a phone number and disconnecting the call before it is answered at no cost) the study staff if they need to reach them. Following a flashed call, the study staff will call participants back at no additional cost to the participant. Flashing is common practice in Uganda and will be utilized by the study participants as needed to reach study staff while in the study. These minimal risks are not likely and will be minimized further by only selecting patients who understand the study and are willing to participate.

6.3. Potential Benefits

Participants may benefit from a positive health outcome associated with a reduction in unhealthy alcohol use. Improved health due to lifestyle changes and/or knowledge gained about health and health conditions may occur as a result of participation. Closer follow-up than standard of care may lead to improved outcomes or patient engagement. Collateral benefits include receipt of refreshments, transportation reimbursements, and the receipt of results from laboratory tests (CD4 cell counts, HIV viral load). PEth biomarker results will not be disclosed to participants due to the lag in testing and the non-routine nature of this test in this population. Otherwise, participants are not promised any direct benefit. The risks to the participants are minimal in relation to the anticipated benefits to the participants and the results of this study could benefit both HIV and alcohol treatment and medical services in Uganda and worldwide.

6.4. Data safety monitoring plan

Day to day data and safety monitoring will be the responsibility of the Principal Investigator. We will follow guidelines set forth by the UCSF IRB regarding AEs. AEs will be reported to the IRBs within 10 days of awareness of the AE. Serious adverse events (SAEs) will also be reported to the NIH and will be reported to the IRBs and the NIH within 2 days.

AEs will be monitored for each subject participating in the study and attributed to the study intervention by the Principal Investigator with review by the physicians/co-investigators according to the following categories:

1. Definite: Adverse event is clearly related to the intervention.
2. Probable: Adverse event is likely related to the intervention.
3. Possible: Adverse event may be related to the intervention.
4. Unlikely: Adverse event is likely not to be related to the intervention.
5. Unrelated: Adverse event is clearly not related to the intervention.

The following scale will be used in grading the severity of adverse events noted during the study:

1. Mild adverse event
2. Moderate adverse event
3. Severe adverse event

In addition to grading the AE, the Principal Investigator will determine whether the AE meets the criteria for a SAE. An AE is considered serious if it:

1. is life-threatening
2. results in in-patient hospitalization or prolongation of existing hospitalization
3. results in persistent or significant disability or incapacity
4. results in a congenital anomaly or birth defect
5. results in death
6. may jeopardize the subject's health and may require medical or surgical intervention to prevent one of the other outcomes listed in this definition, based upon appropriate medical judgment, or
7. adversely affects the risk/benefit ratio of the study

An AE may be graded as severe but still not meet the criteria for a SAE. Similarly, an AE may be graded as moderate but meet the criteria for a SAE. The Principal Investigator and the study physicians/co-investigators will determine the grade of the event as well as its “seriousness.”

Risk assessment

Participation in the EXTEND Study may present minimal risks, including social harm due to loss of confidentiality, disruption of family (e.g., breakup of couples following HIV detection), discrimination (e.g., loss of employment or status in community), physical harm (e.g., acts of physical violence directed at people who have been disclosed as HIV-infected) and embarrassment (e.g., being questioned about alcohol use). Should any of these or other incidents occur, the on-site Field Coordinators will immediately report them to the Principal Investigator, who will in turn report them to the appropriate IRB(s) and to the NIH within ten days of learning of the incident, and notify all study co-investigators. We will ask study participants to return to the research field site as well as provide participants with a palm card containing information on how to contact the local field staff to report such incidents.

The Field Coordinators will be trained to complete descriptions of AEs on an AE reporting form that will then be sent electronically to the US PI. The PI will also report any instances where a US or international IRB takes any action relating to the study. The PIs will make at least two site visits per year to inspect the quality assurance protocol and to review study procedures, including recruitment and data collection.

Interim analyses

No interim efficacy or futility analyses are planned, however, the study team, including the project directors, statistician, co-investigators, field coordinators, and RAs, led by the Principal Investigators, will monitor the progress of the study, participant recruitment, accrual and retention at twice monthly conference call meetings. They will also examine factors external to the study when interpreting the data, such as scientific developments or the new availability of information that could impact the safety of the participants, the performance of the study, or the ethics of the study.

Data Management and Security to Protect Privacy

UCSF, in collaboration with the MUST data management teams, will ensure high quality forms, monitor data quality, and track and link the multiple data sources. The team will jointly develop data collection forms, design the database management system for data entered and for participant tracking, implement procedures for quality control, and provide statistical programming and collaborate in report writing and presentation of study results.

Electronic data will be collected using password-protected laptop computers. The data team will design, develop and maintain the electronic data collection forms, participant and data tracking, and underlying SQL database systems, and implement procedures for data quality control, including multiple checks for entered data. Electronic data collection forms will be designed to read easily, have clear instructions, preprogrammed skip patterns, real-time range checks and internal logic to minimize missing data and resulting in “cleaner” data at capture. The databases will be located on secure, password-protected servers in Uganda and the US.

7. Publication of Research Findings

The findings from this study may be published in a medical journal. No individual identities will be used in any reports or publications resulting from the study. The researchers will publish results of the study in accordance with NIH, UCSF, UNCST, and MUST guidelines.

8. References

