The research assistant will explain that all information provided to study staff will be kept strictly confidential and restricted from access by anyone not involved with the study operations; that all identifying information will be kept separate from their study data (such as the transcript and voice recording from the semi-structured interview); and that all study data will be kept separately from their medical chart. Participants will be informed of the randomization process involved in an RCT and that they will not have the opportunity to choose which arm of the study they will be assigned to. Subjects will be told that they may decline to participate, may refuse to discuss any topic, and may withdraw from the study at any time. Persons unsure about participating will be encouraged to defer enrollment. When a subject agrees to participate, s/he will sign the consent form drafted. Participants will be given a copy of the consent form. If there are literacy reasons why a signature is not appropriate, individuals will be allowed to mark consent forms with an X or thumb print. The consent form includes information on how to contact the study staff to report problems or adverse events, such as violence or other harms related to disclosure that may have occurred in the study.

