For those in the technology booster arm, the counselor will obtain information for the tailoring variables during the in-person session, and will enter them into the technology program interface. The counselor will engage in demonstrations of the SMS and IVR boosters and a discussion of the pros and cons of each, to help participants decide which they prefer, based on their level of literacy, need for confidentiality, and other considerations. After the choice is made, the counselor will provide further training on using SMS or IVR, entering a PIN# to obtain the messages, and responding to the questions. As was effective in increasing engagement in previous tech interventions,¹²⁶ the counselor will send a test SMS or IVR message to Arm 2 participants and watch them enter the PIN# and access and respond to the message, assisting and sending another message as needed. The counselor will also show those choosing SMS how to delete the SMS from their phones after the session. The data manager will monitor SMS/IVR session completion; if there is a 3-week interval with no tech booster session interaction, the data manager will alert the counselor who will call the participant and his/her contacts to verify if the cell phone number is still correct. Participants in both booster arms will receive reminders before they are due for their 2nd in-person counseling session, which will be scheduled to coincide with their next clinic visit.

5.4.2. Intervention delivery in Arm 3

Participants randomized to Arm 3 (SOC) will have no contact with the study counselor for the duration of the trial (9 months). However, at their 9-month study visit, and at the end of their study participation as randomized, they will be offered the intervention and given a choice of the delivery method for the booster sessions. Although the study counselor will deliver the intervention at this time point, we will not collect intervention data associated with this group.

Table 2. RCT study visit and intervention schedule

Study enrollment, baseline questionnaire, DBS collection, and randomization			
Month 0	Arm 1: In-person counseling plus live booster (n=90)	Arm 2: In-person counseling plus tech booster (n=90)	Arm 3: SOC control (n=90)
	In-person counseling session	In-person counseling + tech training	Standard care
Months 1-3	Live booster (every 3 weeks over 12 weeks)	Tech booster (1X to 2x/week over 12 weeks)	---

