5.5. Study visits

Baseline survey and randomization: All participants will undergo collection of contact information, a 30-minute baseline survey, and collection of blood spots for PEth and HIV viral load testing. After these activities, randomization will be conducted by the study coordinator (to keep the RAs blinded) using previously prepared sealed envelopes, in blocks of 9 to spread out the burden of the live boosters. Those randomized to Arms 1 or 2 will be referred to the study counselor for in-person counseling and training on the booster modes. Those randomized to Arm 3 will have no contact with the study counselor.

Six-month follow-up visit. Six months after baseline, we will conduct DBS collection and a quantitative survey, measuring alcohol consumption, and domain characteristics (Table 3).

Nine-month follow-up visit. Nine months after baseline, we will conduct DBS collection and a quantitative survey, measuring alcohol consumption, intervention usability and satisfaction, social desirability, and domain characteristics (Table 3). After data and specimen collection, those in the control arm will be offered the intervention, and will be allowed to choose their preferred method of booster delivery. We will also conduct **IDIs** with 8-12 participants per study arm. These participants will be selected using the a priori categories, with roughly equal numbers of those receiving boosters by SMS and by IVR within Arm 2. The aim of the IDIs will be to explore acceptability and experiences with all three study arms, including the two modes of tech delivery. These interviews will be coded and analyzed using the methods described below (statistical analysis plan).

Individual in-depth interviews at 3-6 months: Following participation in the intervention phase of the trial, a select number of participants (8-12 per study arm) will be invited to participate in a follow-up one-on-one, semi-structured qualitative interview with a research assistant. One third of these participants will participate in the qualitative interview

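### Apart from blood-draw complications, the routes described for adverse events and social harms all depend on the participant coming forward, and the causality scale leaves out harms from study procedures

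*Combined protocol and SAP*

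**What the plan says.** Section 6.4 states: "AEs will be monitored for each subject participating in the study and attributed to the study intervention by the Principal Investigator". It then gives five causality categories, three severity grades, criteria for seriousness and reporting times. It names no question, visit or recall period through which an event would come to light.

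The routes described elsewhere are:

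- Section 5.2.3: "The consent form includes information on how to contact the study staff to report problems or adverse events".
- Section 6.2: "We will provide participants with a small card containing information on how to contact the local field staff to report incidents".
- Section 6.4, Risk assessment: "We will ask study participants to return to the research field site as well as provide participants with a palm card containing information" on contacting local staff.
- Section 6.2, blood draws: "The phlebotomist will report any complications resulting from blood draws to the field study coordinator".

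The first three need the participant to act. The last is the one route that starts with staff.

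Table 3 lists the survey domains at baseline, 6 and 9 months. None covers adverse events, disclosure, violence, family disruption or loss of work. The nearest are the HIV stigma, depression and health-functioning scales.

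All five causality categories are worded against the intervention alone. The last reads "Unrelated: Adverse event is clearly not related to the intervention". Section 6.1 nevertheless names risks from the interviews, the blood draw and loss of confidentiality, and these apply in every arm. Under section 5.4.2, Arm 3 has no study counselor contact for the nine months and is offered the intervention only at the end.

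**The concern.** Section 6.1 ranks loss of confidentiality as the main risk and gives family breakup, loss of employment and domestic violence as possible results. People seldom volunteer such events. A passive system can return a low count whether or not harm occurred.

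Exposure also differs by arm. Table 1 notes that SMS messages stay on the phone. Arms 1 and 2 are asked to bring a support person. Under section 5.4.1, contacts may be called in both booster arms. Home tracking visits (section 5.5) can happen in any arm. Opportunities to tell staff differ as well, so a difference in recorded harms could partly reflect who had someone to tell.

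The causality scale adds a separate gap. If a home tracking visit discloses the HIV status of an Arm 3 participant, the study caused the harm, but no category fits, because that participant has received no intervention.

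**Working it through.** The plan states no figure for harm detection, so there is nothing to reproduce. The check is a contact count, followed by an illustration.

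**Scheduled live staff contacts after baseline** (Table 2)

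| | Arm 1 | Arm 2 | Arm 3 |
|---|---|---|---|
| Live booster calls, every 3 weeks over 12 weeks | 3-4 | 0 | 0 |
| Month-3 counseling session | 1 | 1 | 0 |
| Reminder calls, months 5 and 8 | 2 | 2 | 2 |
| Study visits, months 6 and 9 | 2 | 2 | 2 |
| Total k | 8-9 | 5 | 4 |

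Arm 1 has 12/3 = 4 calls, or 3 if the week-12 call merges with the month-3 session. Arm 2 also has 12 to 24 automated two-way sessions. Not counted are session reminders (mode not stated), ad hoc tracking, and the qualitative interviews, which involve only 8-12 people per arm. The whole difference falls in months 0-3; after that the schedules are identical.

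**Illustration.** Let q be the chance that a harm is mentioned, unprompted, at one contact. The documents give no value, so q is assumed. The chance of capture is 1 - (1 - q)^k. For a harm before the first booster call, with k = 9, 5 and 4:

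| q | Arm 1 | Arm 2, live contacts only | Arm 3 | Arm 1 : Arm 3 |
|---|---|---|---|---|
| 0.1 | 61% | 41% | 34% | 1.8 |
| 0.2 | 87% | 67% | 59% | 1.5 |
| 0.3 | 96% | 83% | 76% | 1.3 |

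For example, at q = 0.1: 1 - 0.9^9 = 0.613 and 1 - 0.9^4 = 0.344, ratio 1.78. With 8 Arm 1 contacts the ratios are 1.7, 1.4 and 1.2.

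**Timing.** A harm after month 3 meets the same contacts in Arms 1 and 3, so the ratio is 1.0. If harms are spread evenly over nine months (also assumed), with Arm 1 contacts at weeks 3, 6, 9 and 12 and month 3, and all arms at months 5, 6, 8 and 9, average capture is:

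- q = 0.1: 33.7% against 27.4%, ratio 1.23
- q = 0.2: 55.3% against 48.4%, ratio 1.14
- q = 0.3: 69.5% against 64.2%, ratio 1.08

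**Arm 2 against Arm 1.** The order depends on what the automated sessions bring in. At q = 0.05, Arm 1 captures 34-37% (k = 8-9). Arm 2 captures 1 - 0.95^5 = 23% from live contacts alone. If each automated session has a 2% chance of drawing a mention, Arm 2 captures 1 - 0.95^5 × 0.98^12 = 39% to 1 - 0.95^5 × 0.98^24 = 52%, which is above Arm 1.

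**The case against.** The strongest defense is that the plan is silent on method and does not rule out active questioning. Section 6.4 commits to monitoring every participant and to following the university IRB's guidance on adverse events. The adverse event form and the live-call script are not in the text available, so prompted questions may exist there. This stands as a limit: the finding concerns what the protocol describes.

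Arm 3 is also not cut off. The no-contact rule concerns the counselor, not research staff. Participants are taught to flash study staff at no cost and are called back, and research assistants are told when a participant attends clinic. These points weaken any claim of large under-detection, but flashing again starts with the participant, and no harm question is attached to the clinic visits.

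Three stronger readings are tempting, and the documents support none of them:

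- *Harms surface only through spontaneous reports.* Blood-draw complications come from the phlebotomist.
- *Arms 2 and 3 will be under-counted, with most harms appearing in the live-call arm.* Arm 2 has the same in-person sessions as Arm 1, free-text or voice replies, counselor call-backs on request, and a counselor call after three silent weeks. For Arm 3, under-counting is a plausible risk and not a certainty.
- *The arms cannot be compared for safety.* Section 5.9 plans no such comparison, and the shared 6- and 9-month visits could carry a common question.

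On causality, a poor fit in the scale does not lose the event. Section 6.4 still requires social harms and other incidents to go to the IRBs and the NIH.

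**Conclusion.** The point holds in this form. Apart from blood-draw complications, every route described for adverse events and social harms relies on the participant, and neither follow-up survey has a harm item. Harms following from the protocol's main risk may be under-detected in all arms. Detection may differ by arm in months 0-3, most clearly for Arm 3, whose first scheduled call is at month 5.

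No size can be stated as fact. The illustrative ratios rest on an invented q, equal true harm in all arms, and the same q for a booster call, a reminder call and a survey visit. They show that the Arm 3 gap could matter early, fades over the full follow-up and is absent for harms after month 3.

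The causality scale has a definite wording gap for harms caused by study procedures, sharpest in Arm 3. This should be corrected, but it does not threaten the efficacy analysis.

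**What to change.** 1. Add one identically worded, closed (yes/no) social-harm and adverse event item for all three arms at the 6- and 9-month visits. It should cover the harms listed under Risk assessment in section 6.4 and come after the timeline follow-back. Details of any yes, including date and severity, should be taken by the Field Coordinator, who already completes the adverse event form. The research assistants are meant to be blinded, and a free-text answer at month 6 could reveal the arm before the month-9 drinking outcome. Asking the item last protects only the same visit, which is why the details should go to someone else.
2. Report counts by arm, with solicited and volunteered reports shown separately. The solicited counts then rest on the same two scheduled questions in each arm.
3. Reword the five causality categories to rate relation to the intervention or to any study procedure.

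The cost is a few minutes at visits that already take place, a form change, more recorded adverse events to process, and a small remaining risk that a bare yes hints at the arm. Harms early in follow-up would still depend on recall at month 6.
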